seminar (HEW) and will examine neural mechanisms of brain connectivity in response to interventions using fMRI biomarkers in 220 older adults with major depression who have been on stable treatment for at least 4 months and still meet criteria for major depression. They will be randomized to adjunctive TCC or HEW. We will establish whether variations in emotional regulation and brain connectivity moderate or predict mood and functional improvement linked with TCC using fMRI markers over the course of the 12 weeks, and will follow maintenance of response in follow-ups at 6 and 12 months (or 24 months if 12 months have passed). 110 subjects will have multimodal MRI evaluation. We anticipate that improvement in depression and cognition will be accompanied by the changes in brain connectivity using fMRI measures of connectivity.

This study incorporates a multidisciplinary investigative team from several centers at UCLA including the Semel Institute ([name], PI), and Ahmanson Lovelace Brain Mapping Center ([name]), as well as benefits from health+wellness education ([name] and statistical expertise ([name], SI-STAT and [name]), and the availability of the cohorts for recruitment from 2 sites. *We plan to assess the ability of the TCC to induce faster and durable remission, and lasting benefits in mood and cognition compared to those in the control group (HEW) as well as the mechanisms (predictors/moderators) of treatment response to each of the elements of combined intervention.*

1. STUDY OBJECTIVES

1.1 Primary Objective

Aim 1: Evaluate the effects of **TCC** versus **HEW** on reduction of depressive symptoms and improvement in the secondary outcomes during the 12-week treatment trial, in addition to 6 and 12 month follow-up (or 24 months if 12 months have passed).

Hypothesis 1: Compared to **HEW**, **TCC** will result in a) greater reduction of depressive symptoms and b) improvement in the cognitive domains of executive function and memory at 12 weeks, 6 months, and 12-month follow-up (or 24 months if 12 months have passed).

1.2 Secondary Objectives

Aim 2. To test whether 12 weeks of **TCC** compared to **HEW** training alter neural regulation of affect during an fMRI affect labeling task and functional connectivity in older adults with depressive symptoms. Imaging biomarkers will predict/moderate treatment response.

Hypothesis 2a: Compared to HEW, TCC will lead to improved functional connectivity in the Default Mode Network as measured with resting state (rs-) fMRI;

Hypothesis 2b: Compared to **HEW**, **TCC** will result in greater activation in the anterior cingulate;

Hypothesis 2c: Imaging biomarkers (hippocampal and anterior cingulate volume, white matter hyperintensity and DMN connectivity) will moderate and predict 1) rate of improvement in symptoms and function; and 2) improvement in cognitive performance.

Aim 3. To examine whether older depressed participants with MCI (LLD+MCI) differ in their cognitive trajectory and neural circuitry compared to older depressed participants without MCI (LLD-MCI) at extended follow-up of 6 and 12 months.

Hypothesis 3a: We hypothesize that changes in episodic memory and executive function will be greater in those with LLD+MCI than in those with LLD-MCI.

Hypothesis 3b: We hypothesize that changes in the default mode/hippocampal-frontal network and in the executive-control and cortico-limbic circuitry will be greater in those with LLD+MCI than in those with LLD-MCI.

Aim 4. *To examine whether greater degradation of neural circuitry is associated with greater cognitive decline.*

Hypothesis 4: We hypothesize that changes in default mode/hippocampal-frontal network and executive-control and cortico-limbic circuitry will be associated with decline in episodic memory and executive function.

Exploratory Aim 1: We will explore the role of treatment-resistance or poor response to the intervention in predicting cognitive outcomes.

Exploratory Aim 2: We will follow a subset of participants (those recruited within 2 years of the initial evaluation) to assess clinical trajectory of mood and cognitive symptoms with 24-month follow-up.

Exploratory aim 3: We will explore the difference in changes in gene expression and peripheral pro-inflammatory cytokines associated with clinical response to the interventions. To use peripheral blood to conduct transcriptome profiling with the same R01 protocols to identify gene expression and peripheral inflammatory biomarkers correlates of clinical response to TCC versus HEW.

Exploratory Hypothesis 3: Treatment response to TCC or HEW will be associated with changes in expression of inflammation, neuroplasticity-related genes and peripheral biomarkers (e.g. cytokines, telomerase), and baseline levels of these genes and cytokines will predict future clinical response.

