Exploratory Hypothesis 2c: Exploratory analysis: Exploratory variables will include hippocampal and anterior cingulate volume and white matter high intensity. To test hypotheses about the relationships between the imaging metrics and the primary outcomes in mood and cognition, we will derive domain summary scores for the 2 cognitive domains of interest, memory, and executive function. We will assess treatment moderator effects of baseline hippocampal and anterior cingulate volume and white matter high intensity on HAMD and memory and executive function domain scores. Statistical evaluation of moderators will be done by including the posited moderator variable as an independent variable and evaluating the moderator x treatment group interaction term in the GLMM models proposed in Aim 1. In addition we will assess the treatment mediator effects of change in DMN connectivity on change in HAMD and memory and executive function domain scores. Mediation effects will be assessed via multiple regression models, where the posited mediator variable is regressed on treatment, outcome is regressed on treatment and the outcome is regressed on the mediator and the treatment. For confirmation of the mediation effect, treatment effects need to be found significant on the outcome and the mediator as well as a decreased treatment effect size on the outcome in the presence of the mediator.

Exploratory aim 1: We will explore the difference in changes in gene expression and peripheral pro-inflammatory cytokines associated with clinical response to the interventions, by comparing the change in these markers between the two intervention groups and by examining how the change in these markers correlate with changes in depression and cognitive scores in the two groups.

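### The claim in Exploratory Hypothesis 3 that baseline gene and cytokine levels predict response has no planned analysis, and no marker-by-arm term tests whether correlates of response differ between TCC and HEW

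*Combined protocol and SAP*

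**What the plan says.** Section 1.2 sets the aim (Exploratory aim 3) as "transcriptome profiling with the same R01 protocols to identify gene expression and peripheral inflammatory biomarkers correlates of clinical response to TCC versus HEW". The hypothesis attached to it has two parts. The first concerns change: "Treatment response to TCC or HEW will be associated with changes in expression of inflammation, neuroplasticity-related genes and peripheral biomarkers". The second concerns prediction: "baseline levels of these genes and cytokines will predict future clinical response".

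Section 9.6 has one paragraph on these markers. It opens "Exploratory aim 1: We will explore the difference in changes in gene expression and peripheral pro-inflammatory cytokines" and names two analyses. One sets TCC against HEW on marker change. The other proceeds "by examining how the change in these markers correlate with changes in depression and cognitive scores in the two groups".

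Just before that paragraph, section 9.6 does specify a baseline-moderator analysis, but for imaging variables only: "We will assess treatment moderator effects of baseline hippocampal and anterior cingulate volume and white matter high intensity on HAMD" and on the two cognitive domain scores. It is run by adding a moderator-by-treatment term to the Aim 1 mixed model.

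Section 9.5.2 lists changes in gene expression and cytokines as exploratory outcomes. Section 6.2.1 schedules blood for RNA and telomerase at screening and at week 12, and makes the genetic portion voluntary.

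**The concern.** A claim that baseline levels predict response needs a model with the baseline level on the right-hand side. Both planned marker analyses use change to week 12 instead. That answers a different question: whether marker and symptoms move together, not whether the marker measured beforehand tells us who will improve.

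The aim also asks about correlates of response to TCC versus HEW. The first planned analysis shows whether the arms differ in marker change. The second, read naturally, gives one correlation per arm. Neither tests whether the link between marker and outcome differs between arms.

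What is at stake is limited but real. Followed as written, the trial would collect baseline blood and then have no prespecified way to answer the prediction half of its own hypothesis. Any later baseline analysis would be post hoc.

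**Working it through.** **Text check: each claim against its planned analysis**

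| Claim (section 1.2) | Analysis needed | Analysis in section 9.6 |
|---|---|---|
| Response goes with marker change | Marker change against outcome change | Present: correlation in the two groups |
| Baseline level predicts response | Baseline marker x time | None |
| Correlates of response, TCC versus HEW | Marker (or marker change) x arm | None; only mean marker change is compared between arms |

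Other places that might close the gap do not:
- The covariates in section 9.6 are demographics and depression course.
- The moderators in section 9.6 are hippocampal volume, anterior cingulate volume and white matter intensity. The mediator is change in DMN connectivity.
- Sections 9 to 9.5 and 10.3.5 contain no gene or cytokine model.
- Section 2.2 and section 6.2.5 mention biomarkers as predictors, but as a goal without a model.

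**Aim number.** Section 1.2 numbers the marker aim Exploratory aim 3 and uses Exploratory Aim 1 for treatment resistance. Section 9.6 calls the marker analysis Exploratory aim 1.

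**What a baseline test could detect.** The documents give no sample size, power, alpha or marker count for this aim, so there is no figure to reproduce. The following is illustrative.

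Inputs:
- 99 completers per arm at week 12 (Sample Size and Population), so 2 x 99 = 198 pooled. This is an upper bound because the genetic portion is voluntary.
- Alpha 0.05, as stated for Aim 1 in section 9.2; two-sided is my assumption.
- Power 80%.
- Number of markers m: assumed.

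Formula (Fisher z with Bonferroni): r = tanh[(z for alpha/m, two-sided, + 0.842) / sqrt(n - 3)].

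For n = 198, sqrt(195) = 13.96:
- m = 1: (1.960 + 0.842)/13.96 = 0.201, so r = 0.20
- m = 20: (3.023 + 0.842)/13.96 = 0.277, so r = 0.27
- m = 20,000: (4.708 + 0.842)/13.96 = 0.397, so r = 0.38

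An assumed m of 1,000 gives 0.34. If only 99 participants contribute (half of completers, or one arm), the values for m = 1, 20, 1,000 and 20,000 are 0.28, 0.38, 0.46 and 0.51.

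**What a marker-by-arm test could detect.** For two correlations with 99 per arm, the detectable difference on the Fisher z scale for one unadjusted marker is 2.802 x sqrt(2/96) = 0.40. As an example, that is r = 0 in one arm against tanh(0.404) = 0.38 in the other. Only large differences between arms are within reach.

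**The case against.** The strongest reply is that this is an exploratory aim, labelled so in sections 1.2 and 9.5.2, and that an exploratory plan need not write out every model. That stands as to severity: no primary or secondary conclusion changes. It does not fill the gap, because the same section does write out the baseline-moderator model for imaging and leaves the blood markers out.

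It is also fair that the hypothesis speaks of response to either intervention, so a marker-by-arm difference is not part of the hypothesis itself. The contrast comes from the wording of the aim.

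A reader might infer several stronger points that the documents do not support:
- **That all marker analysis is done separately by arm.** It is not; the first analysis is a between-arm comparison.
- **That markers significant in one arm only will be reported as specific to TCC.** With a true correlation of 0.20 in both arms and 99 in each, power per arm is 0.51, so exactly one arm would be significant with probability 2 x 0.51 x 0.49 = 0.50. But no section commits to reading results that way. The figure is a reason to specify a direct test, not a description of the plan.
- **That about 1,000 false hits would follow** (20,000 x 0.05; 500 to 1,500 for 10,000 to 30,000 transcripts). Both the transcript count and the 0.05 screen are assumptions. Section 9.6 states no threshold, and the hypothesis is confined to inflammation and neuroplasticity genes and peripheral markers. No multiplicity rule is given for these markers, but that carries little weight in a declared exploratory aim and is not why the prediction claim goes untested.
- **That marker change can never be a predictor.** Change to week 12 precedes the 6-month and later follow-up and could predict those outcomes. Section 9.6 does not plan this, and it would still not test baseline levels.

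**Conclusion.** The concern holds as a minor one. The plan claims prediction from baseline marker levels and specifies no analysis that uses them. It frames the aim as TCC versus HEW and specifies no test of whether the marker-outcome relation differs by arm. The marker aim is also numbered inconsistently between sections 1.2 and 9.6.

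The omission is established by reading the text and rests on no numerical assumption, except that the correlations in the two groups are taken to be one per arm, which is the natural reading. The size of what could be learned does rest on assumptions. A detectable correlation of 0.20 is a best case: one marker, unadjusted, two-sided 0.05, all 198 completers giving blood. With 20 markers it is about 0.27, and with an assumed 20,000 about 0.38. A short list of named markers is therefore the realistic use of these data.

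**What to change.** In section 9.6:

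1. Extend the existing baseline imaging-moderator model to the baseline markers named in Exploratory Hypothesis 3. In the Aim 1 model for HAMD-24, include marker x time for prediction and marker x arm x time for arm-specific prediction, both read at week 12. Alternatively, delete the prediction clause from the hypothesis.
2. Replace the within-group correlations with one model of outcome change on marker change, arm, and marker change x arm. Keep the between-arm comparison of marker change.
3. Make the aim number agree with section 1.2.

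Optional: list the gene sets, cytokines and other markers to be tested first, since the hypothesis names only categories and examples. Report the wider transcriptome with false-discovery control, or label it hypothesis-generating.

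The cost is SAP wording and some extra model runs; both blood draws are already scheduled. The downside is that, with false-discovery control, fewer individual markers will be reported as significant.

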2. BACKGROUND AND RATIONALE

2.1 Background on Condition, Disease, or Other Primary Study Focus

Later-life major depression and depressive symptoms (LLD) have a prevalence of 5-15% in community-dwelling elderly associated with a significant risk of high rates of relapse, morbidity, mortality, and suicide.¹⁻³ Over 60% of the depressed elderly fail to achieve symptomatic remission and functional recovery with pharmacotherapy,^{4,5} accompanied by unremitting cognitive dysfunction and poor health function.⁶⁻⁸ Finding new treatments that enhance functioning of the “aging tsunami” is thus a national imperative.^{9,10} In a recent meta-analysis, Tai Chi appeared to have a significant impact on reducing depressive symptoms compared with the waiting list control groups in older adults (-0.27 (95% CI -0.52 to -0.02, P=0.03).¹¹ In another recent pilot study of older adults with heart failure,¹² Tai Chi practice reduced somatic symptoms of depression. Our preliminary data¹³ demonstrates that Tai Chi Chih (TCC), a “movement meditation,” enhances treatment with the antidepressant, escitalopram, in LLD. As compared to depressed elderly randomized to escitalopram and health education and wellness training (HEW) (n=37), those receiving escitalopram and TCC (n=36) exhibited greater rates of remission, greater clinical, health and cognitive improvement and reduced markers of inflammation, which also prospectively predict depressive symptoms.^{7,14,15} TCC is a brief standardized version of Tai Chi that offers consistent training and practice schedules;^{16,17} posing an important advantage over prior relaxation response-based therapies. Other studies have established that TCC decreases sympathetic output, improves viral immunity and vaccine response, and augments health

functioning in older adults.^{18,19} To date, no studies have addressed the neural mechanisms of response to Tai Chi by investigating emotional and working memory processing, and network connectivity and plasticity in associated brain systems with fMRI. With this proposal, we aim to extend our preliminary findings to evaluate the underlying neural mechanisms of brain plasticity and connectivity in response to TCC compared to HEW during a 12-week acute trial with 6 month and 12 month follow-up (or 24 months if 12 months have passed). We will overcome limitations of our pilot studies by using interventions in older adults with major depression who have been on a stable form of treatment for at least 4 months, but have not achieved remission and still meet criteria for an episode of major depression in order to explore the underlying neural mechanisms of treatment response. We will also compare TCC to the HEW control **group to control for non-specific attention and social support effects (HEW) (active attention control group)**. **This will allow us to estimate the effect sizes of each intervention for future studies, potentially leading to the development of preventive interventions for major depression in older adults.**

Cognitive and neuroimaging biomarkers of LLD and treatment response – what do we know and what can we learn? The identification of state and trait biomarkers of brain function have provided additional knowledge about the mechanisms of geriatric depression.^{20,21} For example, memory or executive function may reflect impairments in 'top down' cognitive control²²⁻²⁵ with *reduced* neural activity in prefrontal cortex (PFC).²⁶ However, *increased* activity in cortical/subcortical regions critical to memory,²⁷ planning²⁸ and attention tasks,²⁹⁻³¹ may be due to compensatory mechanisms relating to cognitive impairments.³²⁻³⁴ These brain activation patterns; as well as reports of decreased striatal response during sequence learning in normal aging,³⁵ but increased activity in the depressed elderly³⁶ may also distinguish normal aging from LLD. Conversely, *tasks of emotional regulation recruit 'limbic' emotional regions such as the amygdala and striatum^{37,38} with a more 'bottom up' pattern of altered processing.^{22,39-44}* Assessment of the neural correlates of emotional processing and affect labeling will complement our other primary (mood) and secondary outcomes (cognitive, health functioning, and fMRI biomarkers of executive function and working memory – Aim 1) to address both "bottom-up" and "top-down" altered processing models. Systems-level functional connectivity may also act as a biomarker of treatment response in major depression as has been demonstrated for an emotional face-matching task specifically in OFC networks following a 4-week antidepressant trial.⁴⁵ Brain activation at rest is not impeded by the subject's cognitive abilities as can limit the investigative power of task-related fMRI and may thus *further reveal which brain systems account for (and predict) depressive symptoms in LLD and vary with respect to treatment outcome*. rs-fMRI allows the study of brain network activity by determining blood-oxygen-level dependent (BOLD)-related synchronous neural activity in spatially distinct brain regions while a person is at rest. Altered connectivity in "default mode" (DMN) network nodes^{46,47} has been reported in major depression⁴⁸⁻⁵¹ and in LLD specifically. DMN connectivity has been shown to link with white-matter hyperintensities (WMH); supporting the hypotheses that disconnection in functionally distinct networks might contribute to depression.⁵² Recent evidence also demonstrates treatment-related changes in resting state connectivity in depression in fronto-limbic regions following antidepressant⁴⁸ and electroconvulsive therapy (ECT).^{53,54} Further, previous work has shown that DMN activity relates to engagement of 'task positive' networks involved in effortful cognition, and that these relationships differ in major depression and associate with maladaptive rumination.⁵⁵ Functional imaging has proven an important tool for visualizing the mechanisms of antidepressant action^{40,56-59-80}, the proposed research will newly address the mechanisms of treatment response to TCC in LLD.⁶⁰ LLD is also linked with *structural brain abnormalities* including global and regional brain tissue reductions, particularly in PFC/ACC, striatal and hippocampal regions,⁶¹⁻⁶⁴ and WMHs, which appear to be associated with *gait imbalance and psychomotor retardation*.⁶⁵⁻⁶⁸ Cross-sectional studies support protective effects of treatment against volume loss in the

hippocampus, amygdala and VLPFC,^{62,63,66,69-71} including in LLD.^{70,71} Early evidence also suggests gray matter variations in fronto-limbic circuits may be predictive of treatment outcome.^{58,72} To complement our fMRI outcome measures (Aims 1 and 2), we will address whether *changes in brain structure in fronto-limbic regions and WMHs, will change or differ as a consequence of TCC or HEW interventions. We will predict future response/relapse, and will relate the results to our other outcome measures. Since longitudinal evidence suggests that 1) antidepressants affect functional connectivity, including in LLD,^{48,53,54,73} and 2) short-term integrative body-mind training or meditation alters functional as well as structural connectivity in the ACC^{74,75} and in auditory/salience and medial visual networks⁷⁶ over short time frames (4-8 wks), it is reasonable to predict that TCC will lead to more pronounced changes in functional connectivity and structural plasticity than HEW (Aims 1-2).*

2.2 Study Rationale

Rationale for duration of interventions and follow-up, and masking procedures: 1) The proposed study uses some elements of the design used in our R21 pilot with novel features of not using psychotropic drugs, double-blind assignment and masking procedures to treatment groups, and the 2 active control conditions to assess the effects of the interventions on the improvement in primary and secondary clinical outcomes, and biomarkers. Based on our pilot study, participants needed 12 weeks to learn and master TCC and thus a 12-week duration is necessary for the active treatment trial.

The post-intervention follow-ups *will include all participants including those who could show worsening of symptoms and discontinue the study* to follow and compare the effect of TCC versus HEW to explore the role of biomarkers as predictors and moderators of the response. Those who agree to follow-up and do not demonstrate response or show worsening will be encouraged to seek treatment alternatives that will be documented in the chart and controlled for in analyses (e.g. types of treatments, dose, and duration). Most participants will be treated in UCLA clinics and their treatment records will be available for review of response patterns. *Follow-up of 6 and 12 months (or 24 months if 12 months have passed) will allow us to document maintenance of symptoms improvement, relapse of major depressive episodes, and compare the rates of maintained remission between the groups, as well as predictor/moderator effects of the biomarkers.*

New knowledge – establishing biomarkers of treatment efficacy: This project will address fundamental gaps in scientific knowledge in identifying biomarkers of response to TCC compared to 2 control conditions HEW. The use of a control group is innovative and will allow us to control for nonspecific support elements in the HEW group. The proposed research extends our pilot work to minimize the use of psychotropic drugs that will allow us examine the mechanism of response to TCC more directly. We will also expand longitudinal assessments up to 24 months to monitor possible relapse into major depressive episode, and worsening of depressive symptoms, that will also integrate response with cognitive performance and with the fMRI probes of emotional processing and working memory and rs-fMRI measures of functional connectivity. Moreover, this study will “zero in” on the mechanisms TCC effect on emotional regulation thus testing relevant stress-responsivity pathways. **Clinical and scientific impact of biomarkers:** Inclusion of biomarkers in studies of clinical response may help *identify the subgroups of older adults who are more likely to benefit from TCC, or those at increased risk for relapse, which would be important for clinical practice.*

Innovation.

Clinical translation. This project will be the first randomized clinical trial to test the CAM mind-body strategy of TCC versus HEW in order to characterize the underlying neurobiological mechanisms of response to TCC. Our treatment model also offers benefits of limiting exposure to multiple drugs, improved physical health, physical strength, agility, and a sense of wellbeing. We have found the TCC program to be very well received by our subjects.

Tai Chi Chih: TCC and other mind-body interventions are directed toward combining aerobic exercise with stress-reduction and structured mindful cognitive approaches that add to improvement in mood and self-esteem. TCC is also known as a "CHI- generating mindful exercise.⁷⁷ The search for the mechanisms of change has focused on two components, relaxation and exercise. In a meta-analysis on the effects of relaxation training, Hyman et al. found that various relaxation response-based interventions led to a reduction of somatic symptoms with additional effects on symptoms of anxiety and depression,⁷⁸ blood pressure,⁷⁹ and recovery from immune-mediated diseases.^{78,80} *As observed in our pilot,⁸¹ TCC in combination escitalopram, appears beneficial for enhancing treatment in LLD, an approach that may readily incorporated into future clinical practice.* Comparing a Chi-generating exercise (TCC) to a comparable non-chi generating exercise is innovative and may shed light on the difference between the two in clinical outcomes (mood, health functioning and quality of life), and the underlying mechanism.

Longitudinal design and long-term follow-up: The goals of behavioral and drug therapies for depression are to improve depressive symptoms and induce remission, thereby preventing relapse and recurrence.^{5,82,83} Remission rates in clinical trials of antidepressant drugs in older adults are around 30-35%.⁸⁴ Extended treatment trials are necessary to optimize interventions for depressive symptoms in older adults.^{85,86} Hence, we propose to use a 12-week acute treatment trial to also satisfy the TCC training objectives. Follow-ups at 6 and 12 months will evaluate maintenance of response/remission or depression relapse (or 24 months if 12 months have passed). Notably, very few studies designed to establish the mechanisms of treatment response in the elderly have included extended follow-up.

Primary and secondary outcome measures: Using fMRI biomarkers of emotional responsivity and affect labeling, and working memory, in addition to clinical measures, during therapeutic manipulation at two time periods is highly innovative. More importantly, this study will examine neural regulation of affect as a putative biological mechanism for the effects of the interventions, thereby advancing psychobiological models of emotional responsivity as predictors of outcomes in geriatric depression. *If our hypotheses are correct, our approach will inform public and clinical practice, and will provide currently missing information about the underlying mechanisms of response to TCC versus controls in geriatric depression.*

Image acquisition and analysis: Multimodal imaging data obtained at 3T will include sequences designed for optimal trade-offs between acquisition time, spatial and temporal resolution, where each modality, not widely applied for the study of LLD, provides unique and complementary information to better evaluate the neurobiological bases of treatment response. Further, we will apply advanced and innovative computational image analysis approaches for integrating data that are noticeably absent in the published literature, focusing on brain aging, connectivity and plasticity and associations with cognition and other health outcomes. *The application of a comprehensive imaging protocol for evaluating treatment response may advance understanding of the mechanisms underlying LLD and treatment-induced brain plasticity and impact clinical practice by providing guidance for delineating biomarkers of treatment response.*

Timeliness: The use of mind-body interventions will be shortly "in-demand" and highly beneficial for the rapidly growing large cohort of aging US "baby-boomers" who have higher rates of depression, and are more likely to use such treatments to prevent or treat the symptoms. Demonstrating the efficacy of such interventions and underlying mechanisms in older adults is becoming a research priority.

Design and outcomes

Interventions and Duration We anticipate screening about 500 subjects to recruit 220 older depressed adults (≥ 60 years old, all of whom will have a range of depressive symptoms and will be on stable treatment (antidepressant or psychotherapy) for at least 4 months. All will meet criteria for major depression and will be randomized to receive 12 weeks of TCC vs HEW used as an adjunct therapy to the stable antidepressant regimen. Follow-ups will confirm clinical endpoints of stable remission and the overall improvement in depression and cognition at Months 6 and 12 (or Month 24 if 12 months have already passed).

Interventions and Duration

Intervention 1 - Tai Chi Chih (TCC): TCC employs “meditation through movement” as a means of helping older adults cope with fatigue, perceived physical limitations, and negative emotional states, which are commonly associated with insomnia.

Intervention 2 - Health and Wellness Education (HEW) control group: This condition will serve as an active control for nonspecific treatment elements such as attention and group support that pose rival explanations for the effectiveness of TCC. Participants will be informed that this intervention is designed to help reduce the severity of depressive symptoms, and all participants will be offered a choice of TCC in the end of the interventions, to balance expectations for the TCC intervention; therefore, reducing the placebo effect.

Duration of Interventions: Each class will be held for 60 minute per day/week. Each TCC class will allow 10 minutes of warm-up (e.g., stretching, breathing), 5 minutes of cool down. Each HEW class will allow 5 min recap from the previous week and 10 min question and answer in the end of the lecture. Homework assignments will be equal in all groups and ask for at least 20 minutes of either TCC, or computer searches on the topics of wellness at home. Participants will be asked to keep diaries of daily exercises, time spent and adherence to the tasks will be compared between the groups, and will be used in the analyses of response.

Sample Size and Population

Subjects: We will recruit 220 older depressed adults aged 60 years old or older, all of whom will have a range of depressive symptoms, meet criteria for an episode of major depression, and will be stable on anti-depressant treatment for at least 4 months. Subjects will be recruited, assessed and randomized according to the scientific protocol and the consent procedures approved by the UCLA Institutional Review Board and the Office of Protection of Research Subjects, as well as the analogous units at participating institutions. We anticipate a maximum of 10% dropout in the first 12 weeks; hence, we will have **99 completers per group at 12 weeks**; and an additional 20% dropout at the end of the follow-up period of 12 months (or 24 months if 12 months have passed) (**88 completers per group**).

